### **5.1.2 Laboratory Evaluations**

#### **5.1.2.1 Baseline Blood Specimen Collection**

Patients enrolled in the ALL cohort will have blood collected at approximately 3, 6, and 12 months once inclusion criteria are met.

A maximum of 25 ml of whole blood will be collected into separate tubes and processed for eventual testing as detailed below. Any subject that is less than 5 kg is not eligible for the study. Therefore, no more than 5 ml/kg of blood will be obtained from any subject during a

---

12-week period. Processed specimens will be stored at -80°C at each site. Approximately every 3 to 6 months, specimens will be batch shipped from participating sites to the central laboratory where antibody testing will be performed. Relevant CHOP specimens will be tested for immune function evaluation. Results will not be available to clinicians in real time. Subjects will have the option to consent to storage of excess blood samples for future non-genetic and genetic studies. These sample remnants will be held at a central laboratory.

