### Study Design:

This study will assemble a prospective, multicenter observational cohort of approximately 115 patients that are completing ALL chemotherapy at one of several pediatric hematology/oncology centers in the US (Children's Hospital of Philadelphia (CHOP), Lurie Children's Hospital of Chicago, Seattle Children's Hospital, Helen DeVos Children's Hospital, Children's Hospital at Vanderbilt, Christus Children's Hospital (Baylor College of Medicine), and Children's Hospital Los Angeles). Consented subjects will have a baseline enrollment visit followed by monthly check-ins via phone and/or chart review to determine if the enrolled patient had any documented viral or bacterial infections or symptoms (Aim 1) and 2) in-person visits at roughly 3, 6, and 12 months post-completion of ALL therapy to obtain blood samples to perform immune function studies (Aim 2).

For comparison of infection rates in patients post-ALL therapy to those of healthy control patients, once the follow-up period for the enrolled ALL cohort patients has ended, a cohort of matched healthy control patients will be assembled. Controls will be selected at a ratio of 3:1, with the full healthy control cohort including up to 330 total patients. The healthy control patients will be followed for the same one-year period as their matched ALL cohort patients. Control patients will be selected from patients who received care at CHOP beginning in 2022 and matched to ALL cohort patients based on age and sex.

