### Setting/Participants:

---

This is a multicenter study at several pediatric hematology/oncology centers in the US (CHOP, Lurie Children's Hospital of Chicago, Seattle Children's Hospital, Helen DeVos Children's Hospital, Children's Hospital at Vanderbilt, Christus Children's Hospital (Baylor College of Medicine), and Children's Hospital Los Angeles). The study cohort will consist of up to 110 evaluable patients prospectively enrolled over the course of this study. Eligible patients include: Children, adolescents, and young adults diagnosed with B or T ALL at age 12 months or older; have completed up-front ALL therapy within the past three months or will complete ALL therapy in the upcoming three months, and are three years of age or older at time of enrollment. Patients who have a diagnosis of infant ALL, evidence of disease relapse, have a history of primary immunodeficiency (except related to Down Syndrome), received a stem cell transplant or cellular immunotherapy, or prior malignancy or condition requiring chemotherapy other than for current ALL diagnosis will be excluded.

All matched healthy control patients will be selected from the Children's Hospital of Philadelphia's Pediatric Research Consortium patient population regardless of where their matched ALL cohort patient was enrolled in the study.

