**FIGURE 1: STUDY DIAGRAM****AIM 1: Incidence of overall infection**

Enrollment visit

- Monthly check-ins to capture data on inpatient and outpatient encounters
- In-person study visits at ~3, 6, and 12 months post-therapy
- Manual extraction from EHR: labs/microbiological data and therapeutic interventions

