### **2.2 Secondary Objective (or Aim)**

Aim 2a: To describe total IgG levels and specific seroprevalence for pneumococcus, varicella, and measles at approximately 3, 6, and 12 months following completion of therapy in patients with ALL

Aim 2b: To describe B and T lymphocyte subset recovery, specifically CD4+ Tfh, using PMBCs at approximately 3, 6 and 12 months following completion of ALL

- Sub-aim: To examine the immune function markers as outlined above in patients who received the monoclonal antibody blinatumomab as part of their ALL treatment regimen versus patients who did not receive blinatumomab.

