### **3.3 Study Population**

#### **3.3.1 Inclusion Criteria for ALL Cohort**

1. Children, adolescents, and young adults ages 3 years to 31 years diagnosed with B or T ALL at age 12 months or older
2. Completed ALL chemotherapy within the past three months or will complete ALL chemotherapy in the upcoming three months (+/- 4 weeks)
  - **Blinatumomab sub-cohort (n = 20-25):** received ALL chemotherapy including the monoclonal antibody blinatumomab
3. Three years of age or older at time of enrollment.

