### **4.2 Visit schedule**

#### **4.2.1 Visit**

Once enrolled, subjects will have a baseline visit, followed by in-person visits at approximately 3, 6, and 12 months. Prior to or at the time of the baseline visit, vaccination records will be obtained. At the baseline and follow-up visits an interim infectious history will be obtained. Patients will have blood drawn for research assays as detailed below at 3-, 6-, and 12-month visits.

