#### **5.1.2.1.3 Laboratory Analysis for Peripheral Blood Mononuclear Cells and CD4+ T-Follicular Helper Cells for ALL cohort participants**

For a subset of enrolled ALL cohort patients (estimated to be 40, including up to 10 patients who received blinatumomab as part of their chemotherapy regimen), blood samples will be processed for cellular immunophenotyping. Blood samples will be collected into sodium heparin tubes at approximately 3, 6 and 12 months following the completion of therapy, processed for peripheral blood mononuclear cells, and cryopreserved. Deep cellular immunophenotyping of the recovering immune system will be performed using high dimensional flow cytometry and T cell receptor (TCR) sequencing in the laboratory of [name] at the Children's Hospital of Philadelphia:

- (1) High Dimensional Flow cytometry: The frequency and phenotype of B and T lymphocytes, with a specific interest in Tfh, will be measured across the three time points and compared to healthy reference controls. The high-dimensional (30-marker) panel has been optimized for use on the Cytek Aurora spectral cytometer and will allow for deep phenotyping beyond Tfh and B cell subsets, resulting in >200 features of returning mononuclear cells.
- (2) Sorting and TCR sequencing of Tfh and non-naïve CD4 T cells: The clonal diversity will be measured by isolating desired cell populations with a BD Aria II cell sorter and extracting nucleic acid for Adaptive Biotechnology (TCR) sequencing. Clonality scores will be tracked over time and compared to the TCR sequence diversity of healthy subjects.

These cellular assays will serve as exploratory measures of immune recovery and vaccine readiness after ALL therapy.

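### The protocol sets conflicting time zeros for the Aim 2 visits and research blood draws (completion of therapy versus enrollment or eligibility), and section 6.3.3 has no rule to resolve them

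*Combined protocol and SAP*

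**What the plan says.** The passages that give a timing for the visits or draws fall into two groups.

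**Completion of therapy as time zero.** The abstract (Study Design) describes "in-person visits at roughly 3, 6, and 12 months post-completion of ALL therapy to obtain blood samples". Figure 1 has "In-person study visits at ~3, 6, and 12 months post-therapy". Section 2.2 sets the Aim 2a measurements "at approximately 3, 6, and 12 months following completion of therapy in patients with ALL", and the abstract's Objectives and Study Measures agree. Section 5.1.2.1.3 times the cellular samples "at approximately 3, 6 and 12 months following the completion of therapy, processed for peripheral blood mononuclear cells, and cryopreserved". Section 3.2.1 ends follow-up about one year after completion.

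**Enrollment or eligibility as time zero.** Section 5.1.2.1, which covers the whole ALL cohort, says patients "will have blood collected at approximately 3, 6, and 12 months once inclusion criteria are met". The visit schedule in section 4.2.1 reads "Once enrolled, subjects will have a baseline visit, followed by in-person visits at approximately 3, 6, and 12 months". Section 4.3 ends observation about one year after enrollment. The visit sentence in section 3.2.1 also starts from enrollment and does not mention completion. Section 5.1.2.1.2, which governs the Aim 2a serum, refers only to blood taken at each visit and so takes whatever timing the visits have.

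**Entry window.** Criterion 2 in section 3.3.1 is "Completed ALL chemotherapy within the past three months or will complete ALL chemotherapy in the upcoming three months (+/- 4 weeks". The abstract (Setting/Participants) gives the same window without the 4-week allowance: "have completed up-front ALL therapy within the past three months or will complete ALL therapy in the upcoming three months".

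**Analysis.** Section 6.3.3 summarises IgG, seroprevalence and lymphocyte subsets at the three nominal timepoints. It states no time zero, no visit window and no rule for assigning a sample to a timepoint. Section 3.2.1 does have the end-of-therapy date abstracted from the record.

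**The concern.** Aim 2 describes recovery by time since therapy. Section 1.2 criticises past studies for not considering patients further removed from therapy, and section 6.4 expects the results to inform revaccination. The label on a sample therefore needs to mean a known time since therapy.

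The sections that read as an enrollment clock are the operational ones: visit schedule, observation period and specimen collection. Section 5.1.2.1.3 does anchor to completion, but it covers only about 40 of the 110 patients. For the Aim 2a serum, the completion anchor appears in the abstract, Figure 1 and the objectives, not in the collection sections. Seven sites could follow different clocks in good faith. Samples at quite different times off therapy would then share a label, and some patients would have no sample at 12 months after therapy.

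**Working it through.** Aim 2 has no power calculation (section 6.4), so there is no figure in the plan to reproduce. The check is interval arithmetic.

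**Inputs**
- Nominal draw times t = 3, 6 and 12 months (all sections).
- Entry offset e = enrollment date minus completion date: -3 to +3 months (section 3.3.1 and abstract).
- Allowance of 4 weeks (section 3.3.1 only): 28 / 30.44 = 0.92 months, so at its widest e runs from -3.92 to +3.92.

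**Formula.** On the enrollment clock, time since completion at a draw is T = t + e. On the completion clock, e = 0 and T = t.

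| Nominal draw | Completion clock | Enrollment clock, +/- 3 months | Enrollment clock, with allowance |
|---|---|---|---|
| 3 months | 3 | 0 to 6 | -0.92 to 6.92 |
| 6 months | 6 | 3 to 9 | 2.08 to 9.92 |
| 12 months | 12 | 9 to 15 | 8.08 to 15.92 |

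**Overlap between patients on the enrollment clock**
- 3 versus 6 months: from 3 to 6 months after completion; with the allowance, from 2.08 to 6.92.
- 6 versus 12 months: the ranges only touch at 9; with the allowance, they overlap from 8.08 to 9.92.
- 3 versus 12 months: none (6 < 9; with the allowance 6.92 < 8.08).
- Within one patient e is constant, so the draws stay 3 and 6 months apart.

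**End of follow-up under section 4.3.** A patient enrolled 3 months before completion and followed for one year from enrollment stops at -3 + 12 = 9 months after completion. A 12-month post-therapy sample, as in section 2.2, falls outside that period. Section 3.2.1 would keep the same patient in follow-up to about 12 months.

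**Illustration.** The documents give no distribution of entry times, so assume e is uniform over a window of total width L.
- SD of T at any label = L / sqrt(12): 6 / 3.46 = 1.73 months, or 7.84 / 3.46 = 2.26 with the allowance, against a 3-month gap between the first two timepoints.
- Chance that one patient's 3-month draw is later off therapy than another's 6-month draw = (L - 3)^2 / (2 L^2): 9 / 72 = 12.5%, or 4.84^2 / (2 x 7.84^2) = about 19% with the allowance.
- Share of nominal 3-month draws taken before completion: 0 without the allowance; 0.92 / 7.84 = about 12% with it.

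**The case against.** The strongest reply is that the intention is clear. Most passages that name an anchor use completion, and the Study Design text in the abstract does so for the blood-draw visits of the whole cohort. The phrase in section 5.1.2.1 can be read as a precondition for drawing blood. Even as a clock it is not the enrollment clock: a patient who meets the other criteria first satisfies criterion 2 about 3 months before completion, which would put the draws at 0, 3 and 9 months. Section 4.2.1 lists visits after baseline without stating what the months are counted from. Aim 2 is descriptive, and actual time since therapy can be calculated if draw dates are kept; section 7.1 collects specimen-collection data.

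Much of this stands. The ranges above apply to a site that uses the enrollment clock, which rests on sections 4.2.1 and 4.3 more than on section 5.1.2.1. The reply does not remove section 4.3, which plainly counts from enrollment and contradicts section 3.2.1. It also does not supply the missing rule in section 6.3.3: the dates permit a correction, but none is planned.

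A reader might also infer three stronger conclusions, which the documents do not support:
- **Aim 2 does not measure time since therapy.** That follows only if every site uses the enrollment clock, and the objectives and several other passages say otherwise.
- **The recovery curve is flattened.** Under a symmetric entry distribution the mean sampling times stay at 3, 6 and 12 months, and a linear mean recovery would be unchanged. What increases is the spread within each label.
- **The blinatumomab comparison is biased.** This needs entry timing relative to completion to differ between recipients and non-recipients, and nothing in the documents shows that it does.

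**Conclusion.** The point holds as an unreconciled contradiction over time zero for the Aim 2 visits, research draws and end of follow-up, with no analysis rule to absorb it. It should be corrected but does not invalidate Aim 2.

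Its size depends on what sites do. If all sites count from completion, the labels are right apart from the undefined tolerance. If a site counts from enrollment, a sample can differ from its label by up to 3 months either way (3.9 with the allowance), and the 3- and 6-month groups overlap between patients. Overlap of the 6- and 12-month groups, and any draw before completion, require the 4-week allowance. Loss of the 12-month post-therapy sample for early enrollees follows from section 4.3. The percentages in the illustration rest on an assumed uniform entry distribution; the ranges do not.

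**What to change.** 1. Reconcile the visit sentence in section 3.2.1 and sections 4.2.1, 4.3 and 5.1.2.1 with the abstract's Study Design, section 2.2 and section 5.1.2.1.3. The end-of-therapy date already abstracted should be time zero for the research draws and for the end of follow-up. Section 5.1.2.1.2 then takes its timing from the corrected visit schedule.
2. In section 6.3.3, assign each sample to a timepoint by actual days since completion, using prespecified non-overlapping windows. The documents give no widths, so the sponsor must set them.
3. Report any sample taken before completion separately.
4. Show the IgG and lymphocyte trajectories against actual days since completion.

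The cost is wording in a few sections and one derived variable, which needs only the end-of-therapy date and the draw date. Samples already drawn can be reclassified in the same way. The downside is that some 3-month samples may move to another window, so the 3-month denominator may fall.

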#### **5.1.2.1.2 Blood Specimen Testing Pneumococcal, Varicella zoster virus (VZV), and Measles virus immunoglobulin G (IgG) and Total IgG for ALL cohort participants**

Blood samples collected at each visit will be processed for serum extraction. Serum will be stored locally and batched shipped to the central laboratory for performance of the following antibody specific assays: Pneumococcal 23 serotype specific IgG (1, 2, 3, 4, 5, 6B, 7F, 8, 9N, 9V, 10A, 11A, 12F, 14, 15B, 17F, 18C, 19A, 19F, 20, 22F, 23F, and 33F). These 23 Pneumococcal serotypes were included because, as a group, they account for approximately 90% of invasive pneumococcal infections. Additionally, varicella zoster virus (VZV) and measles virus IgG assays will be performed. Testing for these assays will be performed by Mayo Clinic BioPharma Diagnostics. Participant results will be compared to standard age specific reference ranges of healthy children.

Serum from these samples will also be used to obtain a total IgG level to aid in interpretation of pneumococcal, varicella, and measles IgG results. This testing will be performed at the CHOP Translational Core Laboratory.

#### **5.1.2.1.3 Laboratory Analysis for Peripheral Blood Mononuclear Cells and CD4+ T-Follicular Helper Cells for ALL cohort participants**

For a subset of enrolled ALL cohort patients (estimated to be 40, including up to 10 patients who received blinatumomab as part of their chemotherapy regimen), blood samples will be processed for cellular immunophenotyping. Blood samples will be collected into sodium heparin tubes at approximately 3, 6 and 12 months following the completion of therapy, processed for peripheral blood mononuclear cells, and cryopreserved. Deep cellular immunophenotyping of the recovering immune system will be performed using high dimensional flow cytometry and T cell receptor (TCR) sequencing in the laboratory of [name] at the Children's Hospital of Philadelphia:

- (1) High Dimensional Flow cytometry: The frequency and phenotype of B and T lymphocytes, with a specific interest in Tfh, will be measured across the three time points and compared to healthy reference controls. The high-dimensional (30-marker) panel has been optimized for use on the Cytek Aurora spectral cytometer and will allow for deep phenotyping beyond Tfh and B cell subsets, resulting in >200 features of returning mononuclear cells.
- (2) Sorting and TCR sequencing of Tfh and non-naïve CD4 T cells: The clonal diversity will be measured by isolating desired cell populations with a BD Aria II cell sorter and extracting nucleic acid for Adaptive Biotechnology (TCR) sequencing. Clonality scores will be tracked over time and compared to the TCR sequence diversity of healthy subjects.

These cellular assays will serve as exploratory measures of immune recovery and vaccine readiness after ALL therapy.

### **5.1.3 Social Determinants of Health Survey**

Participants in this study will be offered the opportunity at the time of enrollment to participate in a brief, one-time Household Survey (Appendix A) intended to capture self-reported data related to social determinants of health and household material hardship (HMH) (e.g., food and/or housing insecurity, lack of access to reliable transportation, etc.). The survey will be hosted within the study REDCap™ database, and the participant (age 18 or older) or parent/guardian will be provided a secure link to access the survey after consenting to participate. Limited English proficiency participants and families will also be eligible to complete the survey but will do so in person via an interpreter if they consent to survey participation.

The Household Survey to be used in this study is based on an abbreviated version of the Household Material Hardship surveys developed by the Dana-Farber Cancer Institute (DFCI) and utilized in clinical trials DFCI 16-001 (NCT03020030), COG AALL1731 (NCT03914625) and COG ANBL1531 (NCT03126916), with demonstrated feasibility of data collection and minimal site or family burden. The Household Survey, developed by the Bona Lab at the DFCI, includes single-item evaluations of self-reported race, ethnicity and health literacy utilizing a validated 1-item screen, educational attainment, HMH, and household income.

Data collected via this survey is intended to be exploratory and will be used to inform further study of possible disparities in infection rates and immune reconstitution.

---

## 6 STATISTICAL CONSIDERATIONS

### 6.1 Primary Endpoint

The primary endpoint for Aim 1 of this study is to determine the incident infection rate in a cohort of subjects in the first year following completion of ALL therapy. Infections will include both clinical and/or microbiologically confirmed infections. All unique infections for a given subject will be captured and included in the final infection rate per person time estimate. Infections will also be reported in subsets of infections such as microbiologically confirmed (i.e., bacteremia, urinary tract infection or pneumonia with a positive sputum culture) or clinically defined infections. Additionally, a specific subset of infections to be described are sinopulmonary infections. This will include a medical encounter for otitis media, sinusitis, or pneumonia for which an antibiotic was prescribed. Infection events for matched healthy control patients will also be captured and used for comparison to the incident infection rate determined for the ALL participants.

The primary endpoint for Aim 2a is the proportion of patients with measles, varicella and pneumococcus antibodies at each study timepoint. Of note, pneumococcal serology results will include 23 serotypes: 1, 2, 3, 4, 5, 6B, 7F, 8, 9N, 9V, 10A, 11A, 12F, 14, 15B, 17F, 18C, 19A, 19F, 20, 22F, 23F, and 33F. Patients with detectable antibody to 50% or more of these serotypes will be considered to have seroprevalence for pneumococcus. This aim will also describe the total IgG levels at each time point at the individual and cohort level. Understanding the total IgG level will inform interpretation of vaccine-specific serology measures.

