The proposed multicenter study will serve to define infection rates in the post-ALL therapy period in children, adolescents, and young adults and define the seroprevalence for vaccine specific antigens as well as presence of lymphocyte subsets at discrete time-points after therapy completion. These data will be immediately informative to clinicians aiming to manage expectations of parents for infection risk in their child post ALL therapy. Additionally, this prospective cohort represents an ideal opportunity to compare management decisions for children regarding timing of vaccination following completion of ALL therapy. Currently, The National Comprehensive Cancer Network (NCCN) recommend that survivors of childhood cancer who received standard (non- HCT) therapy and missed scheduled vaccinations during their cancer therapy should be given all vaccinations that were missed, beginning at 6 to 12 months after completion of treatment. Based upon lower-level evidence, the NCCN recommends that survivors of childhood cancer who were fully vaccinated before diagnosis, and who were treated with chemotherapy or radiotherapy (non- HCT), or both, engage with their provider in a shared decision making to determine approaches to revaccination that might be considered for the individual survivor.

One such approach might be to administer booster doses for all routine vaccinations without checking pre-vaccination titers. A different approach would be to measure antibody titers to determine levels of seroprotection first and then recommending booster doses if inadequate levels of seroprotection are found. Finally, in the absence of data for necessity to administer booster dosing, some centers may elect not to measure antibody titers or provider booster dosing. Not surprisingly, these options have led to variability in practice, even when centers have developed institution-specific guidelines. A survey of Canadian pediatric oncology centers found wide variation in the performance of post-treatment titers and reimmunization practices for survivors of ALL who have not had HCT. Data from this descriptive study will serve to inform future comparative trials designed to optimize vaccination protocols in the period after completion of ALL therapy.

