Outcomes for Aim 2 are descriptive and thus power calculations are not provided. The point estimates for seroprevalence will inform if children retain protection against specific pathogens from vaccination administered prior to their diagnosis of and treatment for ALL. Point estimates for seroprevalence will be described for the entire cohort and by subsets of patient characteristics (e.g., chemotherapy inclusive of blinatumomab). The trajectory of recovery of B and T cell subsets will also be described for the sub-cohort of patients enrolled at CHOP. Differences in trajectories by patient specific characteristic (e.g., chemotherapy inclusive of blinatumomab) will also be explored. These granular descriptive immune function data will inform the need for revaccination in this patient population and if necessary, will provide guidance for the optimal design of revaccination studies.

---

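### The 12-of-23 pneumococcal rule cannot by itself tell retained vaccine protection from other detectable antibody, yet section 6.4 draws that inference

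*Combined protocol and SAP*

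**What the plan says.** Section 6.1 sets the Aim 2a endpoint: "The primary endpoint for Aim 2a is the proportion of patients with measles, varicella and pneumococcus antibodies at each study timepoint". For pneumococcus it adds that "pneumococcal serology results will include 23 serotypes", lists them, and gives the positivity rule: "Patients with detectable antibody to 50% or more of these serotypes will be considered to have seroprevalence for pneumococcus". It names no concentration and does not refer to the child's vaccine.

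Section 5.1.2.1.2 explains the choice of panel: "as a group, they account for approximately 90% of invasive pneumococcal infections". The same section says "Participant results will be compared to standard age specific reference ranges of healthy children". On total IgG, section 6.1 says "Understanding the total IgG level will inform interpretation of vaccine-specific serology measures". Section 6.3.3 will also describe seroprevalence separately for children who had and had not finished their primary vaccine series before chemotherapy.

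Section 6.4 states the use to be made of the results: "The point estimates for seroprevalence will inform if children retain protection against specific pathogens from vaccination administered prior to their diagnosis". It adds that the immune function data will inform the need for revaccination.

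**The concern.** The rule measures whether antibody is detectable across a fixed panel. The conclusion in section 6.4 is about protection that came from earlier vaccines and has been kept. Three things would have to be known to get from one to the other, and the rule contains none of them:

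- which panel serotypes the child was vaccinated against;
- whether the level found is adequate;
- whether the antibody predates therapy or arrived later.

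The rule can therefore mislead in both directions. A child who kept every vaccine antibody may be scored negative because the vaccine covered too few panel serotypes. A child who kept few or none may be scored positive on antibody of other origin. Since the result is meant to guide decisions on revaccination, either error matters.

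**Working it through.** **Step 1: the cut-off.** Section 6.1 lists 23 serotypes, all distinct. 0.50 × 23 = 11.5, so a child needs at least 12.

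**Step 2: what the rule demands of vaccine antibody.** Let k be the number of panel serotypes in the child's pre-diagnosis vaccine. The documents do not give k, so it is an assumption and is ranged.

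- Share of vaccine serotypes that must be detectable if the child has no other pneumococcal antibody: 12/k.
- Fewest vaccine serotypes that can be detectable in a positive child, if every other panel serotype is detectable: max(0, 12 − (23 − k)).

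| k | Share needed from vaccine antibody alone | Fewest vaccine serotypes in a positive child |
|---|---|---|
| 7 | impossible | 0 |
| 11 | impossible | 0 |
| 12 | 12/12 = 100% | 1 (8%) |
| 13 | 12/13 = 92% | 2 (15%) |
| 15 | 12/15 = 80% | 4 (27%) |
| 20 | 12/20 = 60% | 9 (45%) |
| 23 | 12/23 = 52% | 12 (52%) |

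At k of 11 or less, full retention with no other antibody is scored negative, and zero retention can be scored positive.

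**Step 3: illustration.** Let each vaccine serotype be detectable with probability q and each other panel serotype with probability f, all independent. Then P(positive) = P(X + Y ≥ 12), with X ~ Bin(k, q) and Y ~ Bin(23 − k, f). Both q and f are assumed, and independence is a simplification.

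| k | q = 0.9, f = 0.1 (vaccine antibody mostly kept) | q = 0.3, f = 0.7 (mostly lost, other antibody common) |
|---|---|---|
| 7 | 0.01 | 0.80 |
| 10 | 0.19 | 0.61 |
| 12 | 0.62 | 0.46 |
| 15 | 0.97 | 0.26 |
| 20 | 1.00 | 0.06 |

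At small k the rule ranks these two situations the wrong way round. At k of 15 or more it ranks them correctly. How badly it misclassifies therefore depends on k.

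**Step 4: timing.** Section 4.2.1 draws research blood at 3, 6 and 12 months, so there is no earlier research sample to compare with. Section 1.1 says that children who missed doses restart vaccination 6 to 12 months after treatment. It also names boosters as an option for children with a completed series, without giving a time. Samples at 6 and 12 months can thus contain antibody from new doses, and no rule in the plan separates them.

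**Step 5: passive antibody.** Antibody from an immunoglobulin product, if one were given, would count as positive. Section 5.1.1 does not name such products among the abstracted variables; section 7.1 lists only medications in general. Total IgG does not identify the source, because infused IgG raises it too. The documents give no frequency of use, so no size is claimed.

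**The case against.** The best reply is that Aim 2 is descriptive. Its stated objective in section 2.2 is seroprevalence, not protection, and breadth across serotypes that cause most invasive disease is a reasonable thing to describe. Several planned elements also help. The split by primary-series completion in section 6.3.3 ties the result to vaccination at group level. The reference-range comparison addresses level. Vaccination records and serotype-level results are collected.

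Much of this stands. The 12-of-23 figure is a legitimate summary of detectable antibody. But none of these elements enters the positivity rule. The split names neither product nor serotypes, and it does not set aside later doses. The descriptive label does not settle the matter, because section 6.4 itself draws the inference about protection.

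A reader might infer more than the documents support:

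- **That the endpoint can never show retained vaccine immunity.** This goes too far. The primary-series split carries some information, and at larger k with little other antibody the rule tracks detectable vaccine antibody.
- **That the study adopted a seroprotection threshold and then ignored it.** The wording in section 1.2, "measure antibody titers to determine levels of seroprotection first and then recommending booster doses if inadequate levels of seroprotection are found", describes one practice option among several, not this study's endpoint.
- **That trace antibody will count as positive.** The assay's detection limit is not given.
- **That immunoglobulin use inflates seroprevalence by a known amount.** Nothing says any participant receives it. A figure would need an assumed rate of use and an assumed effect on each sample.

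**Conclusion.** The concern holds in a limited form. The section 6.1 rule cannot by itself distinguish retained vaccine protection from other detectable antibody, and section 6.4 needs that distinction. The cut-off of 12 follows directly from the documents. The share of vaccine serotypes required, from impossible at k of 11 or less down to 52% at k = 23, rests on the assumed k and on no other pneumococcal antibody being detectable. The overlap of the 6- and 12-month samples with revaccination follows from sections 1.1 and 4.2.1. The documents allow no estimate of the net error in the reported proportion. The descriptive summary remains usable; what needs correcting is the conclusion drawn from it.

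**What to change.** - **Keep the 12-of-23 proportion**, reported as detectable antibody.
- **Add a measure for any statement about retained protection.** For each child, give the proportion of panel serotypes in the recorded pre-diagnosis vaccine product(s) that meet the age-specific reference level already planned in section 5.1.2.1.2. Name that level in section 6.3.3. Children with no recorded pre-diagnosis pneumococcal vaccine have no denominator and should be shown separately.
- **For all three pathogens, report separately** the samples taken after post-therapy revaccination or after a recorded immunoglobulin product. State in advance how long after such a product a sample is treated this way; the documents give no basis for the length.
- **If product-level records cannot be obtained**, reword section 6.4 so that it speaks only of the presence of detectable antibody.

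No new assay is needed. The cost is product and date fields in REDCap, abstraction time where vaccination records do not name the product, a few lines of SAP text, and some samples set aside from the retained-protection estimate. The fallback costs only the rewording.
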